Intermediary: The 17-item Tampa Scale for Kinesiophobia will be used to measure fear of movement. The MCID for the TSK has been reported to be 4 points in patients with back pain. The 10-item Pain Self-Efficacy Questionnaire will measure the strength and generality of a person's belief in his/her ability to accomplish a range of activities despite pain.

Randomization: To ensure that the number of subjects is about the same in the two arms of the study for each clinical site, the randomization scheme will frequency-match patients in a 1:1 ratio in blocks of assignments stratified by age and type of surgery (i.e., fusion or no fusion). The 4 frequency-matched strata will be as follows: (1) Age 21-59 and fusion; (2) Age 60-90 and fusion; (3) Age 21-59 and no fusion; (4) Age 60-90 and no fusion. Block size will be determined randomly with the patient as the unit of randomization. Randomization will be administered centrally by the Coordinating Center (Vanderbilt) through the REDCap electronic database.

Statistical analysis: All analyses will be both on an "intention-to-treat" and "as treated" basis.

Safety monitoring: A medical monitor will be responsible for monitoring the accumulated interim data as the trial progresses to ensure patient safety, review efficacy, evaluate recruitment, and assess overall data quality.

1. Primary Hypothesis and Principal Objective

The United States has the highest rate of lumbar spine surgery in the world, with rates increasing over 200% in the last decade (1-3). Medicare spends over \$1 billion annually on lumbar spine surgery (4). Despite surgical advances, up to 40% of older adults have persistent pain, disability and functional limitations (5-13). We have found that high fear of movement is a risk factor for increased pain and disability and decreased physical health in patients following lumbar spine surgery (14,15). This finding supports previous work in surgical and chronic low back pain populations (16-24). Brief cognitive-behavioral therapy (CBT) and self-management treatments have proven effective for reducing psychosocial risk factors and improving pain and activity outcomes (25-33). However, these treatments are unavailable or insufficiently adapted for postoperative care.

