6.3.2. Specific Aim 2. The data will be explored numerically and graphically. Group means and corresponding confidence intervals will be calculated for baseline variables, to confirm balance between groups. The characteristics of the patients who are lost to follow-up will be compared to those who complete the follow-up assessments. For each outcome variable, we will fit a multivariable regression model, with site as a covariate. We will explore possible non-linear (quadratic, cubic) effects of the treatment over time. We plan on adjusting for the baseline measurement of the outcome variable, age, type of surgery, site, and depressive symptoms. A random slope over time may be included to allow a separate slope to be estimated for each patient. The primary analysis will be intent-to-treat; missing observations due to drop-out and other reasons not related to the treatments will be handled with multiple imputation methodology. Our use of Bayesian estimation procedures will allow us to easily impute missing data within our models. In most cases, this will allow us to use data with some missing values, and avoid the information loss that is inherent in complete case analysis. Where it is unlikely that values are missing at random, we will include an imputation sub-model that uses available covariates to account for plausible patterns of non-random missingness. Though it is not possible to demonstrate that data are missing at random, including as many predictor variables in the imputation model as possible generally increases the chances that the missing at random assumption (conditional on the covariate values) is reasonable (159). To quantify the effect of the number of sessions completed by study participants on outcomes of interest (i.e., dose-response), we intend to explicitly model the response following session j for subject i in the following linear model: $y_{ij} - y_{i0} = \alpha_0 + \alpha_1 I[\text{session} = j] + \epsilon_i$ where the function I is an indicator for j sessions completed, and $y_{ij} - y_{i0}$ is the change in response after session j from baseline (session 0). This model can be generalized to account for a non-linear response to dose.

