$y_i^{(1)} - y_i^{(0)} = \mu + \beta_1 I(\text{treat}_i) + \beta_2 x_i + \beta_3 x_i I(\text{treat}_i) + \epsilon_i$ where x_i is some covariate of interest from the list above. β_1 , β_2 and β_3 are parameters for the treatment, covariate and treatment-by-covariate interaction, respectively. Sub-groups that show a stronger response to treatment will have relatively large, negative interaction parameter values, indicating that they would reduce the outcome score beyond treatment in the absence of the covariate.

6.4. Missing data. Missing data are a serious concern that complicates the interpretation of the study results. We will address this issue from both a trial conduct and analysis perspective. Regarding trial conduct, we will

1. Limit participant burden and inconvenience in data collection
2. Provide compensation for participation and completion in the study
3. Select high quality investigators
4. Provide pre-study training of investigators as well as on-study reinforcement
5. Monitor and report missing data rates during the trial
6. Emphasize the importance of full participation in the trial during the consent process
7. Collect information on the reasons for missing data
8. Actively engage participants in the study and educate them about the importance of their engagement

9. Collect surrogate information on participants who miss clinic visits
10. Hold regular CBPT meetings to discuss strategies for enrollment and engagement of participation
11. Set targets for acceptable rates of missing data

While these efforts will help to minimize missing data, we recognize that missing data are inevitable.

Our use of Bayesian estimation procedures will allow us to easily impute missing data within our models. In most cases, this will allow us to use data with some missing values, and avoid the information loss that is inherent in complete case analysis. Where it is unlikely that values are missing at random, we will include an imputation sub-model that uses available covariates to account for plausible patterns of non-random missingness. Though it is not possible to demonstrate that data are missing at random, including as many predictor variables in the imputation model as possible generally increases the chances that the missing at random assumption (conditional on the covariate values) is reasonable.

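### Values judged not missing at random are to be imputed from observed covariates, which as worded is still a missing-at-random model, and no analysis tests departures from that assumption

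*Combined protocol and SAP*

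**What the plan says.** Section 6.3.2 makes the primary analysis intent-to-treat and adds that "missing observations due to drop-out and other reasons not related to the treatments will be handled with multiple imputation methodology". Imputation is to be done within Bayesian models. For the harder case, values unlikely to be missing at random, the rule is: "we will include an imputation sub-model that uses available covariates to account for plausible patterns of non-random missingness". The sentence that follows justifies a large predictor set because it "generally increases the chances that the missing at random assumption (conditional on the covariate values) is reasonable". Section 6.4 repeats the rule ("Where it is unlikely that values are missing at random, we will include an imputation sub-model that uses available covariates") and its justification.

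Three other provisions touch on missing data. Section 6.3.2 states that "The characteristics of the patients who are lost to follow-up will be compared to those who complete the follow-up assessments". The conduct list in section 6.4 includes "Collect information on the reasons for missing data" and "Collect surrogate information on participants who miss clinic visits". No analysis is said to use the reasons or the surrogate information.

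**The concern.** The rule is written for the situation in which MAR fails, yet the remedy it names conditions only on observed covariates. Such a model gives missing patients the same outcome distribution as observed patients with the same covariates, and that equality is the MAR assumption.

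The primary outcomes are self-reported disability, pain and general health. If patients who are doing badly leave one arm more often than the other, for reasons the covariates do not capture, the treatment difference is biased. The planned analyses would neither remove all of that bias nor show how much of it the conclusion could withstand. A reader of the eventual report could also take the stated purpose of the sub-model to mean that non-random missingness had been dealt with.

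**Working it through.** **1. What the sub-model can identify.** Let Y be the outcome and X the covariates. Define δ = E(Y | X, missing) − E(Y | X, observed). MAR given X implies δ = 0. A model for Y given X, fitted to observed patients and used to fill in the rest, sets δ to 0. Better covariates can make the true δ smaller. They cannot estimate it, because no outcomes are observed among the missing.

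**2. Whether anything else covers the gap.** No delta-adjusted, tipping-point, pattern-mixture, selection-model or reference-based analysis appears anywhere. The as-treated analysis in the synopsis regroups patients but leaves the missing-data assumption unchanged. The comparison of drop-outs with completers uses observed characteristics only.

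**3. The plan's own retention figure.** The synopsis gives 260 consented and 221 retained at 12 months.
- 221 / 260 = 0.85, so the loss is 39 / 260 = 15%.
- 221 / 2 = 110.5, which agrees with the 110 per arm in section 6.5.

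The denominator matters. Consent is taken before surgery (sections 5.1 and 5.4), and randomization follows the 6-week baseline assessment (section 5.6). Some of the 39 may be lost before randomization, and they cannot cause differential loss between arms. With 221 still retained:
- 10% loss after randomization implies 221 / 0.90 ≈ 246 randomized, so about 14 lost earlier.
- 5% loss implies 221 / 0.95 ≈ 233 randomized, so about 27 lost earlier.

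The documents give no split, so I use 5% to 15%.

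**4. Bias for a given departure.** Higher ODI is worse. Let d be an arm's missing fraction and δ the number of points by which its missing outcomes are worse than MAR predicts (1 = CBPT, 0 = education):

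bias favouring CBPT = d₁δ₁ − d₀δ₀

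The δ values below are assumptions, scaled to the ODI MCID range of 8.2 to 12.8 in section 5.8.1.

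| Scenario | δ = 8.2 | δ = 12.8 |
|---|---|---|
| 15% loss, δ in CBPT only | 0.15 × 8.2 = 1.23 | 0.15 × 12.8 = 1.92 |
| 5% loss, δ in CBPT only | 0.05 × 8.2 = 0.41 | 0.05 × 12.8 = 0.64 |
| 20% v 10% loss, same δ in both arms | 0.10 × 8.2 = 0.82 | 0.10 × 12.8 = 1.28 |
| Equal loss, same δ | 0 | 0 |

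**5. How much covariate imputation leaves.** This is a large-sample simulation (2 million per arm). All inputs are assumptions: ODI SD 18, no true effect, equal loss in both arms, and drop-out in one arm only depending on the unseen outcome at log-odds 0.5 to 1.5 per SD. Missing values are regression-imputed within arm from predictors with correlation R with the outcome. The table shows the absolute bias in the arm difference, in ODI points.

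| Loss | Complete cases | R = 0.5 | R = 0.7 | R = 0.8 |
|---|---|---|---|---|
| 5% | 0.44–1.16 | 0.34–0.89 | 0.23–0.61 | 0.16–0.44 |
| 10% | 0.88–2.2 | 0.66–1.69 | 0.45–1.20 | 0.32–0.86 |
| 15% | 1.3–3.15 | 0.98–2.46 | 0.66–1.74 | 0.48–1.25 |

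At 15% loss imputation removes about 22–25% of the bias at R = 0.5, 45–49% at 0.7 and 60–63% at 0.8. With the same mechanism in both arms the bias was zero to within simulation error (about 0.02).

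**6. What a bias of that order does.** With 110 per arm, SE = SD × √(2/110), which is 1.62 at SD 12 and 2.43 at SD 18. The chance of a false finding for CBPT is Φ(bias/SE − 1.96), against 2.5% without bias.
- Bias 1.23, SD 18: Φ(0.51 − 1.96) ≈ 7%.
- Bias 1.92, SD 12: Φ(1.19 − 1.96) ≈ 22%.

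These apply to the one-arm case at 15% loss.

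**The case against.** The strongest reply is that the form of the sub-model is never given. A Bayesian sub-model could carry a missingness or pattern term as well as covariates, and non-random might loosely mean not completely at random. That stands to this extent: MAR is the natural reading and not an explicit statement. It does not close the gap. If a pattern term is intended, the text names neither it nor its values. If the looser meaning is intended, MAR is the right model but departures from it remain untested.

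The plan also imputes better than a single baseline predictor would suggest. It asks for as many predictors as possible, and appendix 9.4 schedules ODI, BPI, SF-12, TSK, PSEQ and PHQ-9 pre-operatively, at baseline and at 6 months. Many patients missing at 12 months may therefore have a 6-month value, and R of 0.7 to 0.8 is plausible. Section 3.2.2 matches the arms for session frequency, length and therapist contact, and section 3.4 has the same two therapists deliver both, so strong asymmetry in drop-out is less likely. These points limit the size. They do not replace a test.

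Three stronger readings are tempting and should not be drawn:
- **The primary result has no protection.** Good predictors and the conduct measures in section 6.4 reduce bias, and equal informative loss cancels.
- **Treatment-related drop-out is excluded from imputation.** In section 6.3.2 the qualifier about reasons unrelated to treatment may attach only to the other reasons and not to drop-out, and the Bayesian imputation sentence has no such restriction. The wording is ambiguous and needs clarifying.
- **15% of randomized patients will be missing.** The 260 are counted at consent, so 15% is an upper figure for the plan's expected loss.

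**Conclusion.** The concern holds in limited form. As worded, the covariate sub-model assumes MAR given those covariates. It can reduce bias from missingness that depends on the unseen outcome, but cannot account for it, and no sensitivity analysis covers departures from MAR. Confidence in this is high, subject to the sub-model's unstated form.

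The size is much less certain. With SD 18 and informative drop-out in one arm only, across 5% to 15% loss after randomization, roughly 0.3 to 2.5 ODI points remain at R = 0.5 and 0.15 to 1.75 at R = 0.7 to 0.8. The bias is about zero if the mechanism is the same in both arms. The SD, correlations, drop-out slopes, departures and one-arm pattern are all assumptions; the readable text gives no SD or target effect against which to judge these figures. The matter should be corrected, but nothing here shows that the primary result will be biased.

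**What to change.** In sections 6.3.2 and 6.4:

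1. State that all missing outcomes in randomized patients, whatever the reason, are imputed under MAR in the primary analysis. Keep the pre-operative, baseline and 6-month measures as auxiliary predictors. This also removes the ambiguity about treatment-related drop-out.
2. Delete the claim that the covariate sub-model accounts for non-random missingness. Prespecify instead a pattern-mixture sensitivity analysis that shifts imputed values by a delta varied separately in each arm. Ranges can come from the plan's own MCIDs:
   - ODI: 0 to 12.8 points worse (higher).
   - BPI: 0 to 2.1 points worse (higher).
   - SF-12 PCS and MCS: 0 to 10% lower, since higher is better; state what the 10% is taken of.
3. For each outcome, report the delta at which the 95% credible interval comes to include zero. Use the recorded reasons for missingness to judge whether that delta is plausible.

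Fix the ranges before outcome data are seen by arm, because deltas chosen afterwards carry little weight. The cost is a change of wording and a few extra model runs, with no new data or visits. The one downside is that the result may look less certain if it tips at a small delta.

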3.2.1. Treatment Group 1. The CBPT program focuses on a patient-oriented self-management approach to reduce pain and disability and improve physical activity and function, through reductions in fear of movement and increases in self-efficacy. Brief CBT programs for pain developed by Woods and Asmundson (84), Williams and McCracken (69), and Turner et al. (115) and a self-management approach developed for older adults by Lorig (101,102,116,117) provide the basis for the CBPT

program. Sessions cover an introduction and rationale for treatment, deep breathing (118), progressive muscle relaxation (119), graded activity plan, goal-setting (120), distraction techniques (29), automatic thoughts (72), coping self-statements (72), pacing techniques (121), and relapse prevention and symptom management plans (122). Each session builds upon the content of the previous session and weekly action plans are personally tailored based on patient goals. The program consists of six weekly telephone sessions with a trained physical therapist. The first session is approximately 60 minutes and the remaining 5 sessions are approximately 30 minutes (see Appendix 9.2. for more detail). Each patient randomized into the CBPT program will receive a binder to follow along with the study therapist.

Potential Adverse Effects. There are no potential adverse effects specific to the cognitive-behavioral and self-management strategies. There may be distress related to discussing mood and beliefs about pain and functional activity.

3.2.2. Treatment Group 2. The education program focuses on postoperative recovery and is based on web-based modules that were developed and tested in [name] NIH-funded project in patients with musculoskeletal injury (R01AR054009). Educational modules were adapted in collaboration with community-dwelling adults who completed preliminary testing of the CBPT program (109). Sessions address benefits of physical therapy, proper biomechanics after surgery, importance of daily exercise, and ways to promote healing. Education on stress reduction, sleep hygiene, energy management, communication with health providers, and preventing future injury are also provided. The education program is matched to the CBPT treatment in terms of session frequency, length and contact with the study therapist. Each patient randomized into the education program will receive a binder to follow along with the study therapist (see Appendix 9.3 for more detail).

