Accelerometer Analysis. Raw data from the accelerometer will be pre-processed using ActiLife v6.4 software, and integrated into 60-second and 10-second epochs for assessing wear/non-wear intervals and time spent in various physical activity intensities, respectively. Non-wear will be defined as at least 60-minute intervals of “zero” activity counts with 2-min incidental wear intervals allowed. Wear intervals lasting less than 30 minutes will be classified as non-wearing. Total daily wear time will be calculated by subtracting non-wear time from 24 hours. Primary analyses will use total volume of physical activity, expressed as the mean counts per minute over the duration of accelerometer monitoring. Secondary analyses will use percentage of time spent in commonly used domains of physical activity intensity (sedentary, light, moderate, and vigorous).

6.3.3. Specific Aim 3. Separate regression models will be used to explore associations between changes in fear of movement and pain self-efficacy and changes in pain, disability, general health, and physical activity from baseline to 6 and 12 months after surgery for the entire sample. We will construct a mediation model that estimates the effect of the mediation by changes in fear of movement and in pain self-efficacy on outcomes as the result of surgery. This comprises 3 sub-models that relate (1) the treatment to health outcomes directly, (2) the treatment to fear of movement and pain self-efficacy and (3) both the treatment and fear of movement and pain self-efficacy to health outcomes simultaneously. This will demonstrate any mediation effect, if present, by seeing how the relationship between treatment and outcomes changes when the potential mediators are added or removed.

6.3.4. Specific Aim 4. Regression models will be used to explore the interaction between patient characteristics and treatment for each outcome in the entire sample. Important sub-groups will be identified based on the strength of association between the response to treatment (change in outcomes) and each covariate included in the model (i.e., patient age, type of surgery, depressive symptoms). To illustrate, consider the simplified model with just one covariate:

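### The session dose-response equation has no arm term and no covariates, so its coefficient averages CBPT with education sessions and counts prognostic differences between completers and non-completers as an effect of sessions

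*Combined protocol and SAP*

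**What the plan says.** Section 6.3.2 (Specific Aim 2) sets out a dose-response analysis whose aim is "To quantify the effect of the number of sessions completed by study participants on outcomes of interest (i.e., dose-response"). The model is "y_{ij} - y_{i0} = \alpha_0 + \alpha_1 I[\text{session} = j] + \epsilon_i", "where the function I is an indicator for j sessions completed". The one extension foreseen concerns the shape of the curve: "This model can be generalized to account for a non-linear response to dose".

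Two other statements bear on it:

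- Both arms have sessions to count. Section 3.2.2 says: "The education program is matched to the CBPT treatment in terms of session frequency, length and contact with the study therapist". Appendices 9.2 and 9.3 list six sessions for each programme.
- Earlier in 6.3.2, for the main outcome regression, the plan says: "We plan on adjusting for the baseline measurement of the outcome variable, age, type of surgery, site, and depressive symptoms". That list is not written into the dose-response equation.

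The plan's other displayed trial models do carry a treatment indicator. The Aim 4 model in 6.3.4 has "parameters for the treatment, covariate and treatment-by-covariate interaction, respectively", and the sample-size model in 6.5 has the treatment indicator alone.

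**The concern.** The trial exists to contrast two programmes, yet this equation cannot tell a CBPT session from an education session. If only CBPT sessions help, the coefficient is diluted by the education arm.

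The number of sessions completed is also not randomised. It is settled after randomisation by what the patient does and what happens to them. If patients who are doing badly stop early, they will show less improvement whether or not the missed sessions mattered, and an equation without covariates assigns all of that difference to the sessions. The plan nevertheless calls the result an effect. The report could therefore present a session effect that is only selection, or understate a real one in the CBPT arm.

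**Working it through.** The plan states no figure for this analysis, so there is nothing to reproduce. The check has two parts.

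**1. Form of the models, side by side.**

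| Model | Arm term | Arm interaction | Covariates | Introduced as simplified |
|---|---|---|---|---|
| 6.3.2 dose-response | no | no | none | no |
| 6.3.4 Aim 4 | yes | yes | one, for illustration | yes |
| 6.5 sample size | yes | no | none | yes |

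Nothing says that the dose-response model is fitted by arm.

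**2. Illustrative size.** From the documents: 110 per arm with complete follow-up (6.5) and six sessions per arm. Assumed: SD of ODI change 15; a share p of each arm incomplete, spread evenly over 0 to 5 sessions; non-completers worse by a gap g for reasons other than sessions; no session effect. A linear count S stands in for the written indicator.

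- E(S) = 6(1 − p) + 2.5p. At p = 0.20 this is 5.3.
- E(S²) = 36(1 − p) + (55/6)p = 30.63, so Var(S) = 30.63 − 5.3² = 2.54.
- Cov(S, incomplete) = p(2.5 − E(S)) = 0.20 × (−2.8) = −0.56.
- False pooled slope = g × Cov/Var = 5 × (−0.56)/2.54 = −1.10 ODI points per session.
- Pooled SE = 15/√(220 × 2.54) = 0.63.
- z = 1.10/0.63 = 1.74. Chance that the 95% interval excludes zero ≈ Φ(1.74 − 1.96) = 41%.

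The same steps for other incomplete shares, with g = 5:

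| p | Var(S) | False slope | SE | Excludes zero |
|---|---|---|---|---|
| 0.05 | 0.73 | −1.14 | 1.19 | 16% |
| 0.10 | 1.39 | −1.13 | 0.86 | 26% |
| 0.20 | 2.54 | −1.10 | 0.63 | 41% |

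Simulation agrees (16%, 26%, and 38% to 42% across runs). At p = 0.20, a gap of 3 points gives 18% and a gap of 8 points gives 78%.

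**Averaging of arms.** With equal completion, the pooled slope is the mean of the two arm slopes. For a true CBPT slope of −1 and education 0, it is (−1 + 0)/2 = −0.5; simulation gave −0.51, and −1.02 for the arm-by-sessions term. If completion differs by arm, the arm difference itself leaks in. In a separate simulation with no session effect, an arm difference of −8 points and mean sessions of 3.65 (CBPT) against 4.74 (education), the pooled slope was +0.98, and about 0 in each arm once arm terms were added.

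**What the arm-by-sessions model achieves.**

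- SE of the slope difference = 15 × √(2/(110 × 2.54)) = 1.27 (about 1.3 simulated), twice the pooled SE.
- Power for a true CBPT slope of −1: z = 1/1.27 = 0.79, so Φ(0.79 − 1.96) + Φ(−0.79 − 1.96) ≈ 12% (13% simulated). The pooled model in the same setting has z = 0.5/0.63 = 0.79, the same power, for a coefficient half the size.
- If the 5-point gap exists in CBPT only, the slope difference is −1.10 − 0 = −1.10 with no session effect, excluding zero in about 13% of simulated trials. Gaps of 8 (CBPT) and 2 (education) give (8 − 2) × (−0.56)/2.54 = −1.32, excluding zero in 17%.
- Baseline covariates help in part. In a simulation with a false slope of −1.46, a covariate carrying half the variance of engagement left about −0.9; one carrying all of it left about 0.

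**The case against.** The strongest reply is that this is a supplementary analysis. Section 6.3.2 makes intention-to-treat primary, and dose-response appears in no aim, hypothesis, outcome list or power statement. That is correct and limits the weight of the point. A reader might infer that the coefficient will settle how many sessions patients need; no section says so.

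A second reply is that the Aim 2 covariates may be meant to carry over, and that the change score already subtracts baseline. The text does not say that they carry over. The Aim 4 model is flagged as shorthand with "To illustrate, consider the simplified model with just one covariate"; the dose-response model has no such flag. Even with carry-over, covariates would not separate the two programmes.

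A third reply is that the model calculated here is not the one written. The written regressor is an indicator, and the response is that after session j. This stands: the figures show a direction and a plausible order of size, not the behaviour of the written estimator. That response is also not collected, since after baseline outcomes are measured only at 6 and 12 months (5.7, Appendix 9.4). The equation has to be rewritten for that reason as well, and both repairs fit in one edit.

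A fourth reply concerns the remedy. It is tempting to read the education slope as showing what selection and attention alone produce, which would make the CBPT-minus-education difference a clean dose effect. The documents do not support that. Education is an active comparator whose sessions may help, and the programmes ask different things of patients: graded exposure, fear hierarchies and homework in Appendix 9.2, none of them listed in 9.3. Completion may therefore be selected differently by arm. The difference looks unbiased in simulation only when equal selection is imposed.

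**Conclusion.** The point holds, in limited form. As written, the equation pools two programmes and treats a self-selected exposure as if it were assigned. Both faults follow from its form and need no assumed number.

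Their size cannot be taken from the documents, which give no completion rate, SD of ODI change or completer gap. The range of about 15% to 40% false exclusion of zero rests on SD 15, a 5-point gap equal in both arms, 5% to 20% incomplete, and a linear count in place of the indicator. It should not be read as the trial's error rate. Nor should a reader infer that the main result is at risk: the intention-to-treat comparison does not use this model. The correction is worth making because it is cheap and because the analysis, if reported as planned, would carry a label it cannot support.

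**What to change.** Replace the dose-response equation in 6.3.2 with a model for the change from baseline to 6 and to 12 months. Include the treatment indicator, number of sessions completed (0 to 6), their interaction, and the Aim 2 covariates: baseline outcome, age, type of surgery, site and depressive symptoms. Report the two arm-specific slopes and their difference, each with an interval.

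Replace the word effect with exploratory association. State that the difference removes selection only if completion is selected similarly in both arms, and that education sessions may have an effect of their own.

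The cost is a few lines of text and no data beyond the session count the analysis already needs. The downside is precision: under the assumptions above (20% incomplete), the standard error is about 1.3 ODI points per session against about 0.64 pooled, and power for a true CBPT slope of −1 is about 13%. The result will probably be inconclusive and should be presented with its interval and no claim about the number of sessions required.
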